10.5.2 Minimum sample size required

As the main analysis for the primary outcomes (i.e., serious infections and malignancies) will involve a meta-analysis pooling the estimates across all data sources, a meta-analytic approach in sample size estimation was used for each outcome separately. Simulations were used to compute the estimated power to detect pre-specified HR values representing the average population treatment effect (mean) for the anifrolumab exposed group compared to the unexposed group for pre-specified sample sizes. In addition, the minimum sample sizes required to achieve 80% power under specific assumptions were estimated.

⁸ The number of SLE patients provided by the data sources is slightly higher than the estimated average. Thus, current estimates are expected to be a conservative measure of the number of included patients. At the time of interim reports, the number of SLE patients and the assumptions of anifrolumab uptake will be assessed to address the need of protocol adjustments to meet the necessary sample size.

Assumptions and parameters

The main objective of this study is to estimate and compare the risks between the study cohorts in terms of two outcomes – serious infections and malignancies.

Keeping this in mind, the sample analysis methodology relies on estimating power to detect any treatment associated risks between the study cohorts. In this case, we assumed pre-specified HR values of 1.5, 1.8 and 2, as the average population treatment effect (mean) and for variability of this HR, we use two values of assumed standard deviation, 0.1 and 0.2. The idea here is to have a population-level treatment effect distribution of HR with mean values of 1.5 or 1.8 or 2.0, such that from this distribution, every data source randomly samples a unique HR value per simulation run. This approach ensures the variability and heterogeneity which we expect to see from data sources which then necessitates the use of random effects meta-analysis to account for them during the final analysis of this study. Two matching ratios of exposed to non-exposed, 1:1 and 1:3, were chosen. Background rates for the primary outcomes were also varied based on published literature of incidence in the general population and in an SLE population.

Background rates

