For a given matching ratio (exposed: non-exposed) and a given IR, simulations were carried out for a range of overall exposed sample sizes (total sample size of exposed patients across data sources). For each overall sample size (e.g., n = 3000 exposed patients), a proportion of the overall population (country-level sample size) was assigned to each data source (proportions are presented in Table 13). These proportions are based on estimated final sample sizes for the different data sources given the relative sizes of each data source and the prevalence of SLE in each study country. The SLE prevalence in each data source was obtained by literature review (see references in Table 13) The following steps were repeated 1,000 times to get 1,000 simulated 95% CIs for HRs.

Using the simsurv package, survival times were simulated for each data source from a Weibull distribution assuming proportional hazards. The average population-level treatment effect chosen was from a pre-specified list of values -1.5, 1.8 or 2 with assumed variances of SD(HR) = 0.1 and 0.2. The provided sample sizes were taken as the exposed sample size and the non-exposed sample size was calculated as matching ratio * country-level sample size. The average follow-up times were 2 years for serious infections and 5 years for malignancies.

The estimated data source level log(HRs) for exposure status, standard errors and 95% CI were computed by fitting a cox proportional hazards model to the simulated data. The data source level log(HRs) and their standard errors were entered in a random-effect meta-analysis model to compute the pooled HR and its 95% CI. The inverse-variance method was used with the R meta package.

Finally, the proportion of 1,000 simulated runs where the meta-analysis p-value < 0.05, representing the power, was computed. Power was estimated for each pre-specified sample size of exposed group under two different outcome-specific IRs and two allocation ratios (1:1 and 1:3) for three assumed average treatment effects, HRs – (1.5, 1.8 and 2) (Log(HR) values of 0.405, 0.588 and 0.693 in lognormal space respectively) with SD[HR)] – 0.1 (expressed as the geometric coefficient of variation of log(HR) - 0.066, 0.056, 0.05 for three HRs respectively) and 0.2 (expressed as the geometric coefficient of variation of log(HR) - 0.132, 0.11, 0.099 for three HRs respectively In addition, the exact sample size required to achieve 80% power was estimated (Table 13).

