	SD(HR) SD(HR) SD(HR) SD(HR) SD		SD(HR)	SD(HR)					
		=0.1	=0.2	=0.1	=0.2	=0.1	=0.2		
	500	0.265	0.256	0.474	0.516	0.621	0.617		
	1000	0.409	0.433	0.716	0.706	0.832	0.813		
	1500	0.520	0.500	0.813	0.779	0.897	0.902		
0.6 1000	2000	0.586	0.606	0.876	0.854	0.955	0.937		
9.6 per 1000 person-years	2500	0.662	0.644	0.905	0.893	0.958	0.955		
person-years	3000	0.714	0.657	0.930	0.908	0.976	0.972		
	3500	0.750	0.722	0.962	0.923	0.985	0.972		
	4000	0.800	0.753	0.965	0.941	0.985	0.974		
	4500	0.816	0.801	0.971	0.964	>0.999	>0.999		
39.8 per	500	0.583	0.569	0.852	0.829	0.943	0.925		
1000	1000	0.789	0.716	0.958	0.947	0.981	0.985		
person-years	1500	0.882	0.835	0.977	0.975	0.995	0.987		

Table 12 Meta-analysis level power to detect pre-specified target HR under different study size and assumptions of serious infections incidence – allocation ratio 1:3

Abbreviation - HR: hazard ratio; IR: incidence rate; SD: standard deviation

For the malignancy outcome, using an allocation ratio of 1:3, an average follow-up time of 5 years, and an IR of 6.31 per 1000 person-years, the minimum required sample size to achieve 80% power for detecting a pre-specified true HR of 1.5 (geometric mean of 0.425 in lognormal space) from an effect distribution with SD(HR) of 0.2 (geometric coefficient of variation of 0.132 in lognormal space), is approximately **3,195** anifrolumab patients across all countries.

For serious infections, using an allocation ratio of 1:3, an average follow-up time of 2 years, and an IR of 39.8 per 1000 person-years, the minimum required sample size to achieve 80% power for detecting a pre-specified true HR of 1.5 (geometric mean of 0.425 in lognormal space) from an effect distribution with SD(HR) of 0.2 (geometric coefficient of variation of 0.132 in lognormal space), is approximately **1,312** anifrolumab patients across all countries.

The proportional share for each data source was based on the expected number of SLE patients as presented in section 10.5.1. These proportions along with the required country-level sample size to achieve 80% power to detect a pre-specified HR of 1.5 (geometric mean of 0.405 in lognormal space) from an effect distribution with SD(HR) of 0.2 (geometric coefficient of variation of 0.132 in lognormal space) with a 1:3 matching is presented in Table 13.

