10.7.1.6 Meta-analyses

In addition to data source level analyses, results will also be combined in a meta-analysis. Metaanalysis will be performed only for the primary study objectives. The meta-analysis will be performed using aggregated data from all study countries, assuming the country-specific analyses are available for pooling. Prior to conducting the meta-analysis, heterogeneity across the study countries will be assessed using:

- Cochran's Q test (significance level: 0.1). Q is calculated as the weighted sum of squared differences between individual studies and the pooled value across data sources.
- The I² statistic (0% to 40%: might not be important; 30% to 60%: may represent moderate heterogeneity; 50% to 90%: may represent substantial heterogeneity; 75% to 100%: considerable heterogeneity). I² is calculated as follows:

$$I^2 = \left(\frac{Q - df}{Q}\right) \times 100\%$$

Where Q is Cochran's statistic and 'df' is its degrees of freedom. The I^2 is a statistic that estimates the percentage of variance in effects attributable to study heterogeneity rather than sampling error.

• τ^2 statistic: Utilises the Q value to calculate the excess variation across data sources

If high levels of heterogeneity are found to exist, the study design and characteristics in the included local studies will be reviewed and the possible source of heterogeneity discussed. The country-level logHRs and their standard errors will be entered in a random-effect inverse-variance model. Data source-specific results and the overall combined estimate will be presented in forest plots including effect size and 95% CI for each study country included in the analysis. In a sensitivity analysis, the meta-analysis will be done using a fixed-effect model.

Further details regarding the meta-analysis will be presented in the SAP.

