10.7.1.7 Sensitivity analyses

Sensitivity analyses will be conducted for the primary objectives related to malignancies and/or serious infections.

• For both serious infections and malignancies: Patients exposed to anifrolumab will be compared with two groups of patients exposed to SLE SOC: a) patients exposed to SLE SOC biologics (belimumab and rituximab, including biosimilars) and b) patients exposed to SLE SOC non-biologics.

- For malignancies: As the definition of the latency period is subjective, two other latency periods will be evaluated: no latency period and 24 months latency period.
- For serious infections: A comparative analysis of the incidence for each component of the serious infection definition (i.e., infection leading to hospitalisation, use of intravenous antimicrobials and infection-related death) will be conducted, comparing the incidence among patients exposed to anifrolumab versus comparable moderate/severe SLE patients on SOC. However, as these comparative analyses may be limited by small sample size for each of the components of the serious infections' definition, the analyses will only be conducted if feasible.
- Meta-analysis: The main analysis uses a random effects model to pool the effect estimates across data sources assuming that there is heterogeneity amongst the included data sources (i.e., the true effect is different between the data sources). To assess the robustness of this assumption, the meta-analysis will be conducted with a fixed effects model and its results reported as a sensitivity analysis.

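### At the SD(HR) of 0.2 behind 1,312 and 3,195 patients, the 80% power comes from a pooled test whose 95% interval covers about 90–91%

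*Protocol*

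**What the plan says.** Section 10.5.2 defines the target as the mean of a distribution of HRs, with SD(HR) 0.1 or 0.2, from which "every data source randomly samples a unique HR value per simulation run". The four log HRs are pooled in a random-effects model: "The inverse-variance method was used with the R meta package". Power is a count of significant runs: "the proportion of 1,000 simulated runs where the meta-analysis p-value < 0.05, representing the power, was computed". The average HRs simulated are 1.5, 1.8 and 2.0. Both headline sizes, 1,312 and 3,195, are given as "the minimum required sample size to achieve 80% power" at HR 1.5, SD(HR) 0.2 and 1:3 matching. Table 13 splits them as Denmark 5.89%, France 74.56%, Germany 5.40% and Spain 14.16%.

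For the analysis, section 10.7.1.6 states "The country-level logHRs and their standard errors will be entered in a random-effect inverse-variance model" and adds: "Further details regarding the meta-analysis will be presented in the SAP". It also plans Cochran's Q, I² and τ². Section 10.7.1.7 gives the sensitivity analysis for the heterogeneity assumption: "To assess the robustness of this assumption, the meta-analysis will be conducted with a fixed effects model".

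**The concern.** If sources truly differ, the null hypothesis that matches the stated target is an average HR of 1 with sources still differing. With four sources, three of them small, the data say little about the between-source variance. The estimate is often exactly zero, and the interval then shrinks to the fixed-effect one. A power figure obtained that way is partly bought with an interval that is too short.

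The pooled HR is the primary comparative result for objectives 2 and 4 of a safety study. An interval that is too short can produce a false signal of harm or a false finding of lower risk. The protocol reports no run at HR 1 and no coverage, so its own simulation would not have shown this.

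**Working it through.** **Inputs (section 10.5.2, Table 13).** Four sources with the shares above; 1:3 matching. Malignancy: 3,195 exposed, 5 years, 6.31 per 1,000 person-years. Serious infections: 1,312 exposed, 2 years, 39.8 per 1,000 person-years. Two-sided 0.05.

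**Heterogeneity on the log scale.** τ = √ln(1 + (SD/HR)²).
- SD 0.2 at HR 1.5: √ln(1.01778) = 0.133 (the protocol gives 0.132). SD 0.2 at HR 1: √ln(1.04) = 0.198.
- SD 0.1 at HR 1.5: 0.067. SD 0.1 at HR 1: 0.100.

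The protocol gives log-scale values only for HR 1.5, 1.8 and 2.0. Two readings at the null are therefore shown: carry τ over from HR 1.5, or take the same SD(HR) at HR 1.

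**Reproducing the 80%.** Simulation of the protocol's scheme: source log HRs drawn from a normal distribution with SD τ, events from the stated rates and follow-up, inverse-variance random-effects pooling, normal test. At HR 1.5 and τ 0.132, with DerSimonian-Laird / REML variance estimates:
- malignancy, 3,195: 79.4% / 80.4%
- serious infections, 1,312: 79.3% / 80.2%

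A check with Weibull times and fitted Cox models gives 79–81%. Most table cells tried agree within 2 points; the largest gap is Table 9, 5,000 exposed, 1:1 (0.767 against 0.829). Hartung-Knapp does not reproduce 80%; it gives 57–60%.

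**The same test under other conditions.** Both outcomes behave alike; ranges span outcomes and the two estimators.

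| Setting | Result |
|---|---|
| HR 1.5, τ 0.132: coverage of the 95% interval | about 90–91% |
| HR 1, τ 0.132: rejection | about 8–9% |
| HR 1, τ 0.198: rejection | about 12–13% |
| HR 1, τ 0.066: rejection | 4.6–5.3% |
| HR 1, τ 0.10: rejection | 6.3–7.1% |
| HR 1, τ 0: rejection | 3.2–3.6% |

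**Mechanism.** In the null runs with τ 0.132 or 0.198, the between-source variance is estimated as zero in about 47–59%.

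**Power at a true 5% level.** With τ 0.132 under the null, the critical value must rise from 1.96 to 2.27–2.32, and power at the stated sizes is 72–73%. Calibrated to τ 0.198 (critical value 2.63–2.68), it is 63–64%. Hartung-Knapp gives 57–60% power with error still near 7.5%. Its modified form gives 48–50% power with 0.9% error.

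**Why the fixed-effect analysis cannot reveal this (malignancy, HR 1).**
- Event probability: 1 − exp(−0.00631 × 5) = 0.03106. Exposed events 3,195 × 0.03106 = 99.2; comparator events 3 × 99.2 = 297.7.
- Variance the model reports: 1/99.2 + 1/297.7 = 0.01344 (SE 0.116).
- Weights follow the shares, so true variance = 0.01344 + τ² × Σshare². Σshare² = 0.0589² + 0.7456² + 0.0540² + 0.1416² = 0.582.
- τ 0.132: 0.01344 + 0.01742 × 0.582 = 0.0236 (SE 0.154). Effective cut-off 1.96 × 0.116/0.154 ≈ 1.48; rejection about 14%.
- τ 0.198: 0.01344 + 0.03920 × 0.582 = 0.0363 (SE 0.190). Effective cut-off about 1.19; rejection about 23%.

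Its interval is never wider than the random-effects one, so agreement between the two is no reassurance.

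**The case against.** Four points deserve weight.

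First, the protocol does not fix the interval method. It leaves details to the SAP, where the variance estimator and any few-studies correction normally belong. That stands for the final analysis, and silence on the interval is not in itself a fault. It does not rescue the sample sizes, which are fixed here. Of the tests tried, only the unadjusted one gives 80%, and an adjusted interval chosen later would not deliver it.

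Second, no stated number is wrong. Power is defined as the share of runs with p < 0.05, and on that definition 80% is confirmed. A reader might infer that the power was miscalculated, or that false signals occur twice as often as claimed. Neither is supported: the protocol claims no type I error rate.

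Third, a reader might infer that the primary test runs at 8–12% whatever the truth. It does not. If anifrolumab has no effect in any source, the test rejects about 3%. The inflation needs effects that differ by source yet average to 1, and at SD(HR) 0.1 it is small or absent. The 12% further depends on carrying SD(HR) 0.2 to HR 1, which the protocol does not do. With fewer events it shrinks: at assumed follow-up of 1.1 and 2.4 years the range is 6–10%.

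Fourth, the fixed-effect model is not the only safeguard. Q, I², τ² and country-level results are planned. They help the reader, but Q at the 0.1 level flags heterogeneity in only about 12–19% of the null runs at τ 0.132 and 0.198.

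**Conclusion.** The point holds for SD(HR) 0.2, the value on which both headline sizes rest. At that value, 80% power and a valid 95% interval are not available together from the unadjusted test: coverage is about 90–91% at HR 1.5, rejection at an average HR of 1 is about 8–9% (τ 0.132) or about 12% (τ 0.198), and power at a true 5% level is about 72% (τ 0.132). It does not extend to the protocol's smaller heterogeneity value (about 5–7%) or to no heterogeneity (about 3%).

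This rests on the planned sizes, shares, rates and follow-up being met, and on the unadjusted normal test, which is inferred from its reproducing the 80%. DerSimonian-Laird and REML lead to the same conclusion.

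**What to change.** 1. **Section 10.5.2:** rerun the existing simulation at HR 1 with SD(HR) 0.1 and 0.2, saying how SD(HR) is carried to the null. Report rejection rate and interval coverage. Restate the power at 1,312 and 3,195 for the interval that will actually be used.
2. **Section 10.7.1.6:** name the between-source variance estimator and the interval method, chosen from those simulated properties.
3. **Section 10.7.1.7:** do not offer the fixed-effect result as evidence that the pooled interval is robust. Describe it as the average over these four sources.

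A Bayesian random-effects model with a weakly informative prior may be added as a sensitivity analysis with the prior scale varied. It should not be imposed as primary, because the prior scale largely decides the result. For serious infections at τ 0.132 under the null, a half-normal scale of 0.1 gives 7.2% error and a scale of 0.2 gives 2.7%; at scale 0.5, power at HR 1.5 falls to 45%.

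The cost is protocol or SAP wording and a rerun of existing code. The downside is a less favourable stated power at the same sample size.

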10.7.1.7 Sensitivity analyses

Sensitivity analyses will be conducted for the primary objectives related to malignancies and/or serious infections.

• For both serious infections and malignancies: Patients exposed to anifrolumab will be compared with two groups of patients exposed to SLE SOC: a) patients exposed to SLE SOC biologics (belimumab and rituximab, including biosimilars) and b) patients exposed to SLE SOC non-biologics.

- For malignancies: As the definition of the latency period is subjective, two other latency periods will be evaluated: no latency period and 24 months latency period.
- For serious infections: A comparative analysis of the incidence for each component of the serious infection definition (i.e., infection leading to hospitalisation, use of intravenous antimicrobials and infection-related death) will be conducted, comparing the incidence among patients exposed to anifrolumab versus comparable moderate/severe SLE patients on SOC. However, as these comparative analyses may be limited by small sample size for each of the components of the serious infections' definition, the analyses will only be conducted if feasible.
- Meta-analysis: The main analysis uses a random effects model to pool the effect estimates across data sources assuming that there is heterogeneity amongst the included data sources (i.e., the true effect is different between the data sources). To assess the robustness of this assumption, the meta-analysis will be conducted with a fixed effects model and its results reported as a sensitivity analysis.

10.7.1.8 Handling of missing data

The following relates all objectives and all sub-cohorts.

Missing data are those where a variable is directly reported as missing or unavailable, where a variable observation is blank, where the extracted data may not be interpretable, or where the value must be assumed to be missing because of data inconsistency or out-of-range results. Methods commonly used in non-interventional studies for handling missing data, such as imputation, complete case analysis or indicator for missing values, will be considered. The SAP will describe the full details on handling missing data that will include the methods for identifying where missing data methods should be applied, the techniques for identifying the type of missing information and the appropriate imputation methods to be used, if any.

Variables which are only recorded if an event, test, or diagnosis occurs are not eligible for missingness analysis although we acknowledge that these may be missing. For example, if there is no record of an event, it must be assumed that that event did not occur rather than assuming the data are missing because in registry data the fact that a patient did not have the event, is not recorded. All variables relying on the presence of a diagnostic code (i.e., ICD-10) fit this definition.

Lifestyle factors such as smoking, obesity, and alcohol/substance abuse have been identified as having a high possibility of missingness in this study due to the reliance of recording as diagnostic codes or in a specialised registry, therefore we may be unable to adjust estimates for those confounders.

10.8 Quality control

This study will be conducted according to the rules of good pharmacoepidemiology practices (GPP) and the Guideline on good pharmacovigilance practices (GVP) – Module VIII (Rev 1) EMA/813938/2011 Rev 1. All aspects of the study from protocol development to the reporting of the results will be conducted within the work-framework of IQVIA Quality Management System and in accordance with the following manual, operating procedures, and work instructions.

According to the policies and procedures above a quality control plan for the study will be developed and executed, which will include quality control on study methodology, SAP, programming, data management and analysis, and study report including study results and conclusions. Furthermore:

- The principle of the independence of quality control applies.
- IQVIA project management will ensure that individuals responsible for the execution of specific quality control steps will have knowledge, capability and experience which are adequate for the task.
- The result of the execution of the individual steps of the quality control plan will be documented, and include the required corrective actions, if any.
- The execution of any required corrective action will be documented.
- The executed quality control plan will be subjected to a final review and approval for sufficiency and completeness by the IQVIA project management team.
- The project management team will also ensure that IQVIA employees assigned to the project are trained on protocol and project-specific procedures, as per IQVIA procedure.

The study will be conducted as prescribed in this protocol. Revisions to the protocol would be approved by the principal investigator and AstraZeneca. All changes to the protocol shall be documented as protocol amendments and when necessary, such protocol amendments are delivered to relevant ethics committees and register holders.

The study protocol has been written following the Code of Conduct by the European Network of Centres of Pharmacoepidemiology and Pharmacovigilance (ENCePP) (European Medicines Agency, 2018). The protocol also follows the key elements of the Guideline for GPPs by International Society for Pharmacoepidemiology (ISPE).

IQVIA, the principal investigator, the MAH and individuals acting on their behalf commit to adhere to the rules of the ENCePP Code of Conduct in their entirety.

For information on storage of records, archiving of the statistical programming will be performed to generate the results and possible audits. Due to the study type (observational study using secondary databases) on-site monitoring will not be performed.

